14.5 Physical Examination

Physical examination is performed at Screening and Week 12/ET visits.

Physical examination results (normal, abnormal, and not done) at Screening and Week 12 will be summarized in a frequency table by treatment group, body system and visit.

14.6 Other Safety Variables

14.6.1 Suicidal Ideation and Behavior

GCAS is assessed at Screening, Baseline, Weeks 2, 4, 8, 12/ET and Follow-up (if applicable) visits.

The number and percentage of subjects for each GCAS rating (0-4) based on clinician's assessment will be tabulated by treatment group and visit. The number and percentage of subjects reporting any post-Baseline GCAS score of 3 or 4 based on clinician's assessment will also be tabulated for each treatment group.

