  - place the subject at undue risk from study drug or undergoing study procedures; or
  - interfere with the interpretation of safety or efficacy evaluations performed during the course of the study

13. Has participated in or is participating in a clinical trial of any investigational drug, device, or intervention, and within 4 weeks (or 5 half-lives, whichever is longer) of the Baseline visit
14. Subject with sensitivity to pimavanserin or its excipients
15. Subject has previously participated in a clinical study with pimavanserin
16. Subject is judged by the Investigator or the Medical Monitor to be inappropriate for the study
17. Subject is receiving skilled nursing care for any medical condition other than dementia (skilled nursing care includes procedures that can only be administered by a registered nurse or doctor, such as [but not limited to] intravenous administration of medication, procedures related to insertion or care of suprapubic catheters, and nasopharyngeal/tracheostomy aspiration)
18. Has a body mass index (BMI) of <18.5
19. Has an abnormal vitamin B12 result at Screening or within the prior 12 months prior to Visit 1 (Screening) that has not been successfully treated
20. Has a Global Clinician Assessment of Suicidality (GCAS) score of 3 or 4 based on Investigator's assessment of behavior within the last 3 months at Screening or since-last-visit at Baseline

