### **6.2.8 Suicidal Ideation and Behavior**

The Global Clinician Assessment of Suicidality (GCAS) will be used to assess the occurrence of treatment-emergent suicidal ideation and behavior.

The GCAS is a clinician-rated, 5-point scale that is designed to rate the subject's suicidality based on the report of the subject, the report of the study partner/caregiver, and the clinician's global assessment. Ratings can be 0 (Absent), 1 (Feels life is not worth living), 2 (Wishes he/she were dead or any thoughts of possible death to self), 3 (Suicidal ideas or gesture), or 4 (Attempt at suicide). The Investigator will record a subject rating, a partner/caregiver rating, and a clinician rating. For a rating of 3 or 4 based on the clinician's assessment, the date of event will be recorded. At Visit 1 (Screening) lifetime suicidality and suicidality for the past 3 months will be assessed and at all other visits, suicidality since the previous visit will be assessed.

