### **9.8.6 Suicidal Ideation and Behavior**

The number and percentage of subjects for each GCAS rating (0-4) based on clinician's assessment will be tabulated by treatment group and visit. The number and percentage of subjects reporting any post-baseline GCAS score of 3 or 4 based on clinician's assessment will also be tabulated for each treatment group.

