5.2.8 Global Clinician Assessment of Suicidality (GCAS)

Global Clinician Assessment of Suicidality (GCAS) is assessed at Screening, Baseline, Weeks 2, 4, 8, 12/ET and Follow-up (if applicable) visits.

The GCAS will be used to assess the occurrence of treatment-emergent suicidal ideation and behavior. The GCAS is a clinician-rated, 5-point scale (0–4) that is designed to rate the subject's suicidality based on the report of the subject, the report of the study partner/caregiver, and the clinician's global assessment. Ratings can be 0 (“Absent”), 1 (“Feels life is not worth living”), 2 (“Wishes he/she were dead or any thoughts of possible death to self”), 3 (“Suicidal ideas or gesture”), or 4 (“Attempt at suicide”). The Investigator will record a subject rating, a partner/caregiver rating, and a clinician rating. For a rating of 3 or 4 based on the clinician's assessment, the date of event will be recorded. At Screening visit lifetime suicidality and suicidality for the past 3 months will be assessed, at all other visits suicidality since the previous visit will be assessed.

Missing GCAS scores will not be imputed.

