The laboratory values will also be summarized in shift tables by treatment group, to determine the number and percentage of subjects with values classified as below (low), within (normal) and above (high) normal ranges at Week 4 and Week 12 visits relative to the same classification at the Baseline visit. The shifts from Baseline to overall post-Baseline minimum and overall post-Baseline maximum will also be presented. For the by-visit shift summary, the denominator is the number of subjects with non-missing values at Baseline and the given visit for the given parameter and treatment group. For the summaries of shift to the overall post-Baseline minimum or maximum, the denominator is the number of subjects with non-missing Baseline and at least 1 post-Baseline value for the given parameter and treatment group. For hemoglobin, hematocrit and uric acid, the shift summaries will be presented for each gender as well as for both genders combined.

Number and percentage of subjects with potentially clinically important (PCI) laboratory values at Week 4, Week 12 visits and overall post-Baseline will be summarized by treatment group and by Baseline status (all and within normal range) for selected parameters. PCI criteria are listed in [Table 5](#) and [Table 6](#). For the overall post-Baseline summaries, all post-Baseline values will be considered, including unscheduled and out of window values. Subjects with multiple PCI values for a given parameter will be counted only once for that parameter. For the by-visit summary, the numerator for the percentage is the number of subjects with a post-Baseline PCI laboratory value for the given parameter, visit and treatment group, and the denominator is the number of subjects with non-missing values for the given parameter, visit and treatment group. For the overall post-Baseline summary, the numerator for the percentage is the number of subjects with at least 1 post-Baseline PCI laboratory value for the given parameter and treatment group and the denominator is the number of subjects with at least 1 post-Baseline laboratory value for the given parameter and treatment group. For hemoglobin, hematocrit and uric acid, the count and percentage of subjects with PCI values will be presented for each gender as well as for both genders combined. Subjects with any PCI values will be presented in an additional listing.

Table 5 Criteria for Potentially Clinically Important Laboratory Values – Hematology and Chemistry

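### Treatment-emergent increases to a GCAS rating of 1 or 2 cannot be read from any planned table: the only across-visit summary counts ratings of 3 or 4, and no GCAS summary relates a rating to Baseline

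*SAP*

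**What the plan says.** SAP 5.2.8 gives the purpose of the scale: "The GCAS will be used to assess the occurrence of treatment-emergent suicidal ideation and behavior". Protocol 6.2.8 says the same and defines the levels. Rating 1 is feeling that life is not worth living, rating 4 is an attempt, and the two middle levels read "2 (Wishes he/she were dead or any thoughts of possible death to self), 3 (Suicidal ideas or gesture)".

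SAP 14.6.1 plans two summaries. The first is by visit: "The number and percentage of subjects for each GCAS rating (0-4) based on clinician's assessment will be tabulated by treatment group and visit". A second runs across visits: "The number and percentage of subjects reporting any post-Baseline GCAS score of 3 or 4", again on the clinician's assessment. Protocol 9.8.6 plans the same pair.

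Four other provisions matter:

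- Exclusion criterion 20 (protocol 4.1.2) bars this finding when the subject is screened: "Global Clinician Assessment of Suicidality (GCAS) score of 3 or 4 based on Investigator's assessment of behavior within the last 3 months". It applies the same cut at Baseline, to the time since the last visit. Ratings of 1 and 2 do not bar entry.
- After Screening, each GCAS rating covers the time since the previous visit (SAP 5.2.8).
- SAP 5.3.1 and 5.3.2 let early-termination and unscheduled assessments compete for visit slots. The one nearest the target day enters the by-visit summary.
- SAP section 5 states that all collected data will be listed.

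For laboratory values, SAP 14.2 goes further: "The shifts from Baseline to overall post-Baseline minimum and overall post-Baseline maximum will also be presented".

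**The concern.** A treatment-emergent summary has to show, subject by subject, what is new or worse since Baseline. The by-visit table shows how many subjects hold each rating at a visit. It does not show whether a rating of 2 at Week 8 was already present at Baseline, or whether the subjects rated 2 at Week 4 and at Week 8 are the same people. The across-visit count does follow the subject, but only at 3 or 4.

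So for ratings 1 and 2, including the wish to be dead, the plan yields no number of subjects who got worse. Efficacy is now descriptive only (SAP section 1), so the safety description is a main remaining output of the trial. A difference between arms in movement from 0 to 2 would have to be pieced together from listings.

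**Working it through.** The plan states no rate, power or event figure for GCAS, so there is nothing to reproduce. The check has three parts.

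**1. What each planned GCAS output can answer**

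| Question | By-visit table, 0-4 | Any post-Baseline 3 or 4 | Listing |
|---|---|---|---|
| How many are rated 1 or 2 at a given visit? | Yes | No | By hand |
| How many are ever rated 1 or 2 after Baseline? | No | No | By hand |
| How many rose from Baseline to 1 or 2? | No | No | By hand |
| How many ever reach 3 or 4? | No | Yes | By hand |

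**2. How loosely the by-visit table bounds the number of new cases**

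Inputs:

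- Arm size: 111 randomized 1:1:1 (SAP 3.1, 3.5), so n = 111/3 = 37, assuming equal arms.
- Post-Baseline clinic visits: Weeks 2, 4, 8 and 12, so V = 4. The telephone follow-up, where it applies, would add a fifth.
- Assumption, since the documents give no rates: x subjects are rated 1 or 2 at Baseline and x at each of the four visits, with complete data and ratings 1 and 2 pooled.

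Formulas:

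- Ever rated 1 or 2 post-Baseline: minimum x (the same subjects throughout), maximum min(n, V·x) (different subjects at each visit).
- Newly rated 1 or 2: minimum 0 (they are the Baseline subjects), maximum min(n − x, V·x) (none was rated 1 or 2 at Baseline).

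| x (percent of 37) | Ever 1 or 2 | Newly 1 or 2 | Upper limit, percent |
|---|---|---|---|
| 1 (2.7) | 1 to 4 | 0 to 4 | 4/37 = 10.8 |
| 2 (5.4) | 2 to 8 | 0 to 8 | 8/37 = 21.6 |
| 4 (10.8) | 4 to 16 | 0 to 16 | 16/37 = 43.2 |

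Within each row the by-visit table is identical at both ends of the range.

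**3. A rating that reaches neither table**

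The Week 4 window is Days 22 to 42 with target Day 29 (SAP 5.3, Table 4). Suppose a subject is rated 0 on Day 29 and 2 at an early-termination visit on Day 40.

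- Distances from target: |29 − 29| = 0 and |40 − 29| = 11. SAP 5.3.2 selects Day 29, so the by-visit table shows 0.
- The rating of 2 is below the 3-or-4 cut, so the across-visit count omits it.

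The rating then appears only in a listing. SAP 5.3.2 does keep every post-Baseline value for extreme-value safety summaries, but no GCAS summary below 3 is of that kind. The loss depends on timing: an early-termination visit on Day 43 would fall in the Week 8 window and be counted there.

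**The case against.** The strongest reply has five parts.

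- **Ratings 1 and 2 are tabulated.** A reader might infer that they are never counted. The documents do not support that: the by-visit table gives every rating by arm, and all data are listed. In a randomized trial the arms can be compared at each visit without any shift. This stands. What is missing is the count of subjects in whom the rating is new.
- **The 3-or-4 line needs no Baseline comparison.** A reader might infer that it fails as a treatment-emergent count. If exclusion criterion 20 is applied, a post-Baseline 3 or 4 is already new relative to Baseline. This stands too. One caveat: footnote d of the assessment schedule, in both documents, does not list GCAS among the eligibility checks repeated at Baseline. That does not match criterion 20, and the two should be reconciled.
- **The cut does capture ideation.** On the scale's own labels, suicidal ideas are rating 3. It would be wrong to say that the summary misses suicidal ideation as a whole; the gap is at ratings 1 and 2.
- **Shift tables are not universal in this SAP.** Physical examination gets only a by-visit frequency table (14.5). True, but laboratory values (14.2), vital signs (14.3) and QTcF (14.4) are all related to Baseline, and GCAS has an expressly treatment-emergent purpose.
- **The added table has its own weaknesses.** The Baseline rating covers only the time since Screening, so a subject rated 2 in the three months before Screening but 0 at Baseline would count as new. The worst of up to five later ratings set against one Baseline rating also raises the proportion with any increase. Both are correct. They act on all arms alike and call for a footnote; they are no reason to omit the table.

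**Conclusion.** The point holds as a reporting gap at ratings 1 and 2. No planned table gives the number of subjects whose rating rises from Baseline to those levels, and a rating of 1 or 2 that is not selected for its visit window enters neither GCAS table. It might surface as an adverse event if the investigator reports it as one, but nothing in the documents requires that.

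The size is modest. The SAP and protocol agree with each other, no efficacy conclusion is touched, and with 111 subjects the information could be extracted by hand from listings. The ranges above (for example 0 to 8 of 37) rest on assumed by-visit counts. They show how little those counts constrain the answer and do not predict what will be seen.

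A reader might also infer that a lower cut would bring a worthwhile gain in power. The documents give no GCAS rates from which to derive one, and SAP section 1 plans no hypothesis testing. The case for the change is descriptive completeness.

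**What to change.** In SAP 14.6.1, and in protocol 9.8.6 to match, add by treatment group:

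1. A shift table of Baseline clinician rating (0-4) against worst post-Baseline clinician rating (0-4), using all post-Baseline assessments, including unscheduled and early-termination ones, whether or not they were selected for a visit window.
2. The number and percentage of subjects with any post-Baseline clinician rating above their Baseline rating.

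Keep the by-visit table and the 3-or-4 line. Add a footnote that the Baseline rating covers only the period since Screening, and that taking the worst of several post-Baseline ratings raises the any-increase proportion in every arm, so only the comparison between arms is informative.

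The cost is a few lines of SAP and protocol text and one extra descriptive table with small cells. The ratings are already collected at every visit.

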15 CLINICAL PHARMACOKINETIC AND PHARMACODYNAMIC ANALYSES

For pimavanserin-treated subjects in the Pharmacokinetics Analysis Set, plasma concentration data for pimavanserin and its metabolite (AC-279) will be listed and summarized using descriptive summary statistics by visit and treatment group.

Concentrations that are below the limit of quantification (BLQ) will be displayed as "BLQ" in the data listings and imputed as 0 for computing summary statistics.

16 INTERIM ANALYSIS

No interim analysis is planned in this study.

17 DATA MONITORING/REVIEW COMMITTEE

An independent Safety Monitoring Committee (SMC) will review interim safety data including data on AEs and SAEs. The SMC will be independent of the Sponsor and the Investigators and will be empowered to recommend stopping the study due to safety concerns. The roles and responsibilities of SMC members and planned frequency of meetings are detailed in the SMC Charter.

An independent statistician (and/or programmer) not affiliated with the Sponsor will produce unblinded statistical outputs and provide these outputs to SMC members using a secure method. The Sponsor and the Investigators will remain blinded until the official unblinding of the database at the end of the study. The outputs presented to SMC members will include but not limited to summaries of enrollment and disposition, demographics and Baseline characteristics, medical and AD histories, concomitant medications, study drug exposure, all adverse events (including deaths, SAE and AEs leading to discontinuation), vital signs, laboratory test results, and ECG parameters. Subject profiles, boxplots of Baseline and most extreme post-Baseline values for clinical laboratory data, and listings of AEs and potentially clinically important laboratory and QTcF results will also be provided to SMC members for their review.

18 COMPUTER METHODS

All data summaries will be performed using Version 9.3 (or newer) of SAS® (SAS® Institute, Inc., Cary, North Carolina) on a suitably qualified and validated environment.

Validation and quality control of the tables, listings and figures containing the results of the data summaries will follow appropriate standard operating procedures.

19 CHANGES TO ANALYSES SPECIFIED IN PROTOCOL

None.

21 APPENDICES

21.1 Summary of Version Changes

Version No:	Document History Description of Update	Author	Effective Date
		██████████
